5.6.1.1.11 Fever

Subjects should be carefully monitored for signs and symptoms of fever, chills, or pyrexia. All attempts should be made to rule out other causes such as metastatic disease, hypersensitivity, bacterial or viral infection.

Episodes of fever have been observed in subjects receiving dabrafenib monotherapy or in combination with trametinib (see dabrafenib and dabrafenib + trametinib combination IBs), as well as in subjects receiving pembrolizumab. In a minority of cases the fever which occurred with dabrafenib and trametinib was accompanied by symptoms such as severe chills, dehydration, hypotension, dizziness or weakness.

Fever accompanied by hypotension, dehydration requiring IV fluids, renal insufficiency, or severe (\geq Grade 3) rigors/chills, in the absence of an obvious infectious cause should be reported as an SAE.

Subjects should be instructed on the importance of immediately reporting febrile episodes. In the event of a fever, the subject should be instructed to take non-steroidal anti-pyretics as appropriate to control fever. In subjects experiencing fever associated with rigors, severe chills, dehydration, hypotension, etc., renal function should be monitored carefully.

Guidelines regarding management and dose reduction for fever considered to be related to study treatment are provided in [Table 26](#).

Table 26 Management and Dose Modification Guidelines for Fever

Adverse Event	Adverse Event Management	Action and Dose Modification
Fever ^a	
1st Event^b:
 
 • Clinical evaluation for infection and hypersensitivity^c • Laboratory work-up^c • Hydration as required^d • Administer anti-pyretic treatment if clinically indicated and continue prophylactic treatment^{e,f} 
2nd Event^g:
 
 • Clinical evaluation for infection and hypersensitivity^c • Laboratory work-up^c • Hydration as required^d • Within 3 days of onset of fever 
 • Optimize anti-pyretic therapy^e 	
1st Event:
 
 • Interrupt dabrafenib • Continue trametinib and pembrolizumab • If fever does not resolve within 48 hours, hold trametinib and pembrolizumab • Once fever resolves to baseline, restart study treatment at the same dose level 
 • If fever was associated with dehydration, hypotension, or renal insufficiency, reduce dabrafenib by one dose level 
2nd Event:
 
 • Interrupt dabrafenib • Continue trametinib and pembrolizumab • If fever does not resolve within 48 hours, hold trametinib and pembrolizumab • Once fever resolves to baseline, restart study treatment at the same dose level 
 • If fever was associated with dehydration, hypotension, or

Adverse Event	Adverse Event Management	Action and Dose Modification
	
Subsequent Events:
 
 • Clinical evaluation for infection and hypersensitivity^c • Laboratory work-up^c • Hydration as required^d • Within 3 days of onset of fever: 
 • Consider oral corticosteroids (i.e., prednisone 10 mg) for at least 5 days or as clinically indicated^f • Optimize oral corticosteroid dose as clinically indicated for recalcitrant fever^g • If corticosteroids have been tapered and fever recurs, restart steroids • If corticosteroids cannot be tapered consult Sponsor 	
renal insufficiency, reduce dabrafenib by one dose level
 
Subsequent Events:
 
 • Interrupt dabrafenib and pembrolizumab • Continue trametinib • Once fever resolves to baseline, restart pembrolizumab at the same dose level, restart dabrafenib reduced by one dose level^g • If dabrafenib must be reduced to <75 mg BID, permanently discontinue dabrafenib

a. Fever is defined as a body temperature equal to or above 38.5 Celsius or 101.3° Fahrenheit.
 
b. For subjects experiencing fever complicated by rigors, severe chills, etc., a clinical evaluation and laboratory work-up is mandatory for each event; anti-pyretic treatment should be started immediately at the first occurrence and prophylactic anti-pyretic treatment is recommended. For subjects experiencing rigors/chills without fever, work-up and supportive care, including interruption of study treatment, are recommended.
 
c. Thorough clinical examination for signs and symptoms of infection or hypersensitivity is required; laboratory work-up should include full-blood-count, electrolytes, creatinine, BUN, CRP, liver-function tests, blood culture, and urine culture.
 
d. Oral hydration should be encouraged in subjects without evidence of dehydration. Intravenous hydration is recommended in subjects experiencing fever complicated by dehydration/hypotension.
 
e. Anti-pyretic treatment may include ibuprofen, or suitable anti-pyretic medication according to institutional standards. Acetaminophen should be used with caution, especially in subjects with elevated liver enzymes. Prophylactic anti-pyretic treatment may be discontinued after three days in the absence of fever.
 
f. In subject experiencing fever complicated by rigors, severe chills, etc., which cannot be controlled with anti-pyretic medication, oral corticosteroids may be started at the 2nd event and doses should be gradually increased for subsequent events.
 
g. Dabrafenib should be reduced by one dose level after three episodes of fever complicated by rigors, severe chills, etc., which cannot be managed by best supportive care and increasing doses of oral steroids. Escalation of dabrafenib is allowed if no episode of fever is observed in the 4 weeks subsequent to dose reduction.
		

5.6.1.1.12 Cardiovascular Events

Cardiovascular adverse events have been seen in subjects receiving either dabrafenib, trametinib or both in combination. See the IBs for additional information. Pembrolizumab dose modification guidance and stopping criteria for myocarditis are provided in [Table 10](#).

5.6.1.1.12.1 Left Ventricular Ejection Fraction (LVEF)

Decreases of the left-ventricular-ejection-fraction (LVEF) have been observed in subjects receiving trametinib monotherapy and in combination with dabrafenib. Therefore, ECHOs must be performed to assess cardiac ejection fraction in regular intervals as outlined in the protocol. All ECHOs will be collected.

Dose modification guidance and stopping criteria for LVEF decrease are provided in [Table 27](#).

Table 27 Dose Modification Guidelines and Stopping Criteria for LVEF Decrease

Clinic	LVEF-drop (%) or CTCAE grade	Action and Dose Modification
Asymptomatic	Absolute decrease of >10% in LVEF compared to baseline and ejection fraction below the institution's LLN	
 • Interrupt dabrafenib and trametinib and repeat ECHO within 2 weeks^a • If the LVEF recovers within 4 weeks (defined as LVEF ≥LLN and absolute decrease ≤10% compared to baseline) 
 • Consult with the Sponsor and request approval for restart • Restart treatment with trametinib reduced by one dose level • Restart dabrafenib at previous dose level^b • Repeat ECHO 2, 4, 8 and 12 weeks after re-start; continue in intervals of 12 weeks thereafter • If LVEF does not recover within 4 weeks 
 • Consult with cardiologist • Permanently discontinue trametinib • Repeat ECHO after 2, 4, 8, 12, and 16 weeks or until resolution • Consult with Sponsor^d
Symptomatic^c	Grade 3: resting LVEF 39-20% or >20% absolute reduction from baseline Grade 4: resting LVEF <20%	
 • Permanently discontinue trametinib • Discontinue dabrafenib • Report as SAE • Consult with cardiologist • Repeat ECHO after 2, 4, 8, 12, and 16 weeks or until resolution^e • Consult with Sponsor^c

Abbreviations: CTCAE = Common Terminology Criteria for Adverse Events; ECHO = echocardiogram; LLN = lower limit of normal; LVEF = left ventricular ejection fraction;
 
a. If ECHO does not show LVEF recovery after 2 weeks, repeat ECHO 2 weeks later.
 
b. If recurrent episodes of LVEF reduction occur with dabrafenib treatment, consult medical monitor.
 
c. Symptoms may include: dyspnea, orthopnea, and other signs and symptoms of pulmonary congestion and edema.
 
d. Once LVEF recovers, restarting dabrafenib can be considered in consultation with Sponsor.
 
e. Once LVEF recovers, including resolution of symptoms, restart of dabrafenib only, can be considered in consultation with Sponsor.
		

5.6.1.1.13 Hypertension

Increases in blood pressure have been observed in subjects receiving trametinib.

5.6.1.1.13.1 Monitoring of Hypertension

All blood pressure assessments should be performed under the following optimal conditions:

1. the subject has been seated with back support, ensuring that legs are uncrossed and flat on the floor
2. the subject is relaxed comfortably for at least 5 minutes
3. restrictive clothing has been removed from the cuff area and the right cuff size has been selected
4. the subjects arm is supported so that the middle of the cuff is at heart level
5. the subject remains quiet during the measurement.

In subjects with an initial blood pressure reading within the hypertensive range, a second reading should be taken at least 1 minute later, with the 2 readings averaged to obtain a final blood pressure measurement. The averaged value should be recorded in the eCRF.

Persistent hypertension is defined as an increase of systolic blood pressure (SBP) > 140 mm Hg and/or diastolic blood pressure (DBP) > 90 mm Hg in three consecutive visits with blood pressure assessments from two readings collected as described above. Visits to monitor increased blood pressure can be scheduled independently from the per-protocol visits outlined in Study Procedures. Ideally, subsequent blood pressure assessments should be performed within one week.

Asymptomatic hypertension is defined as an increase of SBP >140 mm Hg and/or DBP >90 mm Hg in the absence of headache, light-headedness, vertigo, tinnitus, episodes of fainting or other symptoms indicative of hypertension.

5.6.1.1.13.2 Management of Hypertension

For subjects experiencing an increase in systolic and/or diastolic blood pressure that is persistent and may be associated with the study treatment, recommendations for the clinical management of hypertension are described in [Table 28](#).

Table 28 Management and Dose Modification Guidelines for Hypertension

Hypertension	Action and Dose Modification
(Scenario A) 
 • Asymptomatic and persistent^a SBP of ≥ 140 and < 160 mmHg, or DBP ≥ 90 and < 100 mmHg, or 
 • Clinically significant increase in DBP of 20 mmHg (but still below 100 mmHg). 	
 • Continue study treatment at the current dose • Adjust current or initiate new antihypertensive medication • Titrate antihypertensive medication(s) during the next 2 weeks as indicated to achieve well-controlled^b BP • If BP is not well controlled within 2 weeks, consider referral to a specialist and go to scenario (B).
(Scenario B) 
 • Asymptomatic SBP ≥ 160 mmHg, or DBP ≥ 100 mmHg, • or • Failure to achieve well-controlled BP within 2 weeks in Scenario A 	
 • Interrupt dabrafenib and trametinib if clinically indicated • Adjust current or initiate new antihypertensive medication(s) • Titrate antihypertensive medication(s) during the next 2 weeks as indicated to achieve well-controlled BP • Once BP is well controlled^b, restart study treatment reduced by one dose level
(Scenario C) 
 • Symptomatic^c hypertension or 
 • Persistent SBP ≥ 160 mmHg, or DBP ≥ 100 mmHg, despite antihypertensive medication and dose reduction of study treatment 	
 • Interrupt dabrafenib and trametinib • Adjust current or initiate new antihypertensive medication(s) • Titrate antihypertensive medication during the next 2 weeks as indicated to achieve well-controlled BP • Referral to a specialist for further evaluation and follow-up is recommended • Once BP is well controlled, restart study treatment reduced by one dose level
(Scenario D) 
 • Refractory hypertension unresponsive to above interventions or hypertensive crisis. 	
 • Permanently discontinue dabrafenib and trametinib • Continue follow-up per protocol.
Abbreviations: BP = blood pressure; DBP = diastolic blood pressure; mmHg = millimetres mercury; SBP = systolic blood pressure; a. Hypertension detected in two separate readings during up to three consecutive visits b. Well-controlled blood pressure defined as SBP ≤ 140 mm Hg and DBP ≤ 90 mm Hg in two separate readings during up to three consecutive visits. c. Symptomatic hypertension defined as hypertension aggravated by symptoms (e.g., headache, light-headedness, vertigo, tinnitus, episodes of fainting) that resolve after the blood pressure is controlled within the normal range.	

5.6.1.1.14 Prolonged QTc

Guidelines for dose modification and stopping criteria due to QTC-prolongation are provided in [Table 29](#).

Table 29 Withholding and Stopping Criteria for QTc-Prolongation

QTc-Prolongation ^a	Action and Dose Modification

 • QTcB ≥501 msec, OR • uncorrected QT>600 msec, OR • QTcB>530 msec for subjects with bundle branch block 	
 • Interrupt dabrafenib and trametinib until QTcB prolongation resolves to grade 1 or baseline • Test serum potassium, calcium, phosphorus, and magnesium. If <LLN correct with supplements to within normal limits • Review concomitant medication usage for a prolonged QTc • If event resolves, restart dabrafenib and trametinib at current dose level^b • If event does not resolve, permanently discontinue study treatment • If event recurs, permanently discontinue study treatment

Abbreviations: msec = milliseconds; QTcB = QT interval on electrocardiogram corrected using the Bazett's formula
 
a. Based on average QTc value of triplicate ECGs. For example, if an ECG demonstrates a prolonged QT interval, obtain two or more ECGs over a brief period, and then use the averaged QTc values of the three ECGs to determine if study treatments should be interrupted or discontinued. If the QTc prolongation resolves to grade 1 or baseline, the subject may resume dabrafenib and/or trametinib if the investigator and Sponsor agree that the subject will benefit from further treatment.
 
b. If the QTc prolongation resolves to grade 1 or baseline, the subject may resume dabrafenib and/or trametinib if the investigator and Sponsor agree that the subject will benefit from further treatment.
	

5.6.1.1.15 Hepatic Laboratory Abnormalities

The following AE terms, if considered ≥ Grade 2 or if requiring dose modification or use of systemic corticosteroids for treatment of the AE, are considered ECIs and should be reported to the Sponsor within 24 hours of the event:

- Hepatitis
- Hepatitis, Autoimmune
- Transaminase elevations
- Bilirubin abnormalities
- Any increase in Liver Function Tests (LFTs) ≥ grade 3 or any increase from grade 0 to grade 2

Subjects should be carefully monitored for signs and symptoms of elevations in AST, ALT, total bilirubin, fever, malaise and/or upper quadrant abdominal pain. All attempts should be made to rule out other causes such as metastatic disease, progressive liver disease, viral hepatitis, alternative drug toxicity, infectious causes and/or myositis.

Drug Induced Liver Injury (DILI)

In addition, the event must be reported as a Drug Induced Liver Injury (DILI) ECI, if the patient meets the laboratory criteria for potential DILI defined as:

- An elevated alanine transaminase (ALT) or aspartate transaminase (AST) lab value that is greater than or equal to three times (3X) the upper limit of normal (ULN) and
- An elevated total bilirubin lab value that is greater than or equal to two times (2X) ULN and
- At the same time, an alkaline phosphatase (ALP) lab value that is less than 2X ULN,
- As a result of within-protocol-specific testing or unscheduled testing.

Note that any hepatic immune ECI meeting DILI criteria should only be reported once as a DILI event. Dose modification guidance and stopping criteria for hepatic laboratory abnormalities are provided in [Table 10](#) (for pembrolizumab) and [Table 30](#) (all study drugs).

Table 30 Management and Dose Modification Guidelines for Hepatic Laboratory Abnormalities

Event	Adverse Event Management	Action and Dose Modification
AST or ALT \geq 5.0x ULN	
 • Monitor hepatic laboratory tests more frequently until returned to baseline values (consider weekly) • For Grade 2 AST, ALT, or bilirubin elevations, treat with 0.5-1 mg/kg/day methylprednisolone or oral equivalent and when LFT returns to grade 1 or baseline, taper steroids over at least 1 month, consider prophylactic antibiotics for opportunistic infections 	
 • Hold pembrolizumab when AST or ALT $>$3.0x to 5.0x ULN and/or total bilirubin $>$1.5x to 3.0x ULN • Resume pembrolizumab when LFT returns to \leqGrade 1 or baseline • Permanently discontinue pembrolizumab for patients with liver metastasis who begin treatment with Grade 2 elevation of AST or ALT, and AST or ALT increases \geq50% relative to baseline and lasts \geq1 week

Event	Adverse Event Management	Action and Dose Modification

AST or ALT >5.0xULN to ≤8.0xULN without bilirubin elevation (defined as total bilirubin^a ≤2.0xULN, or direct bilirubin ≤35%)
	
 • Consider appropriate consultation and liver biopsy to establish etiology of hepatic injury, if necessary • Treat with high-dose intravenous glucocorticosteroids for 24 to 48 hours. When symptoms improve to Grade 1 or less, a steroid taper with dexamethasone 4 mg every 4 hours or prednisone at 1 to 2 mg/kg should be started and continued over no less than 4 weeks. • If serum transaminase levels do not decrease 48 hours after initiation of systemic steroids, oral mycophenolate mofetil 500 mg every 12 hours may be given. Infliximab is not recommended due to its potential for hepatotoxicity. • Several courses of steroid tapering may be necessary as symptoms may worsen when the steroid dose is decreased. 	
 • Discontinue pembrolizumab if AST/ALT >5.0x ULN and/or total bilirubin >3.0xULN • Hold dabrafenib, and/or trametinib if (any criteria are met): 
 - AST/ALT >5.0x ULN - AST/ALT >3x ULN AND total bilirubin >2x ULN - Total bilirubin > 3x ULN • Interrupt dabrafenib and/or trametinib until recovery to Grade ≤1 • After consultation with Sponsor, dabrafenib and/or trametinib may be restarted reduced by one dose level • If no recovery to grade ≤1 within 2 weeks, permanently discontinue study treatment

AST or ALT >3.0 x ULN with concomitant elevation in bilirubin (defined as total bilirubin^a ≥2.0 x ULN with direct bilirubin >35%) OR meeting any liver chemistry stopping criteria (see 5.6.1.1.15.1)
	
 • Same as grade 3 	
 • Permanently discontinue all study treatment

Abbreviations: CTCAE = Common Terminology Criteria for Adverse Events a. Serum bilirubin fractionation should be performed if testing is available. If testing is unavailable and a subject meets the criterion of total bilirubin flix ULN, then the event should be promptly reported as an SAE.
		

Note: in the event of a drug-induced liver injury (DILI) adverse event (as outlined in the study protocol), please follow the DILI guidance outlined in the site Administrative Binder.

5.6.1.1.15.1 Liver Chemistry Stopping Criteria

These liver chemistry stopping and follow-up criteria have been designed to assure subject safety and evaluate liver event etiology in alignment with the FDA Guidance for Industry – Drug-Induced Liver Injury: Premarketing Clinical Evaluation (July 2009, www.fda.gov).

Liver chemistry stopping criteria 1-5 are defined as:

1. AST/ALT ≥3xULN and bilirubin ≥2xULN (>35% direct bilirubin) (or AST/ALT≥3xULN and INR>1.5, if INR measured)

NOTE: If serum bilirubin fractionation is not immediately available, study treatment should be discontinued if $AST/ALT \geq 3xULN$ and bilirubin $\geq 2xULN$. Serum bilirubin fractionation should be performed if testing is available. If testing is unavailable, record presence of detectable urinary bilirubin on dipstick, indicating direct bilirubin elevations and suggesting liver injury.

2. $AST/ALT \geq 8xULN$
3. $AST/ALT \geq 5xULN$ but $<8 xULN$ persists for ≥ 2 weeks
4. $AST/ALT \geq 3xULN$ if associated with the appearance or worsening of symptoms of hepatitis or hypersensitivity such as fatigue, nausea, vomiting, right upper quadrant pain or tenderness, pyrexia, rash or eosinophilia.
5. $AST/ALT \geq 5xULN$ but $<8 xULN$ and cannot be monitored weekly for >2 weeks.

When any of the liver chemistry stopping criteria 1 - 5 is met, do the following:

- **Immediately discontinue subject from** study treatment
- Report the event to Sponsor **within 24 hours** of learning its occurrence
- Complete the liver event CRF and SAE data collection tool if the event also meets the criteria for an SAE
 - All events of $ALT \geq 3xULN$ **and** bilirubin $\geq 2xULN$ ($>35\%$ direct bilirubin) (or $ALT \geq 3xULN$ and $INR > 1.5$, if INR measured; INR measurement is not required and the threshold value stated will not apply to subjects receiving anticoagulants), termed 'Hy's Law', **must be reported as an SAE**.
 - NOTE: if serum bilirubin fractionation is not immediately available, study treatment should be discontinued if $ALT \geq 3xULN$ **and** bilirubin $\geq 2xULN$. Serum bilirubin fractionation should be performed if testing is available. If testing is unavailable, **record presence of detectable urinary bilirubin on dipstick**, indicating direct bilirubin elevations and suggesting liver injury
- Complete the liver imaging and/or liver biopsy CRFs if these tests are performed
- Perform liver event follow up assessments, and monitor the subject until liver chemistries resolve, stabilize, or return to baseline values as described below
- Follow up for overall survival is required following discontinuation from study treatment.
- Do not rechallenge with study treatment.

In addition, for subjects meeting liver stopping criterion 1:

- Make every reasonable attempt to have subjects return to clinic **within 24 hours** for repeat liver chemistries, liver event follow up assessments, and close monitoring
- A specialist or hepatology consultation is recommended
- Monitor subjects twice weekly until liver chemistries (ALT, AST, alkaline phosphatase, bilirubin) resolve, stabilize or return to within baseline values.

For subjects meeting any of the liver stopping criteria 2 – 5:

- Make every reasonable attempt to have subjects return to clinic **within 24-72 hrs** for repeat liver chemistries and liver event follow up assessments
- Monitor subjects weekly until liver chemistries (ALT, AST, alkaline phosphatase, bilirubin) resolve, stabilize or return to within baseline values;
- Subjects meeting criterion 5 should be monitored as frequently as possible.

5.6.1.1.15.2 Liver Event Follow-up Assessments

For subjects meeting any of the liver chemistry stopping criteria 1 – 5, make every attempt to carry out the **liver event follow up assessments** described below:

- Viral hepatitis serology including:
 - Hepatitis A IgM antibody
 - Hepatitis B surface antigen and Hepatitis B Core Antibody (IgM)
 - Hepatitis C RNA
 - Cytomegalovirus IgM antibody
 - Epstein-Barr viral capsid antigen IgM antibody (or if unavailable, obtain heterophile antibody or monospot testing)
 - Hepatitis E IgM antibody.
- Blood sample for pharmacokinetic (PK) analysis, obtained within 10 days of last dose. Record the date/time of the PK blood sample draw and the date/time of the last dose of study treatment prior to blood sample draw on the CRF. If the date or time of the last dose is unclear, provide the subject's best approximation. If the date/time of the last dose cannot be approximated OR a PK sample cannot be collected in the time period indicated above, do not obtain a PK sample. Instructions for sample handling and shipping are in the SPM.
- Serum creatine phosphokinase (CPK) and lactate dehydrogenase (LDH).

- Fractionate bilirubin, if total bilirubin $\geq 2 \times \text{ULN}$.
- Obtain complete blood count with differential to assess eosinophilia.
- Record the appearance or worsening of clinical symptoms of hepatitis, or hypersensitivity, such as fatigue, nausea, vomiting, right upper quadrant pain or tenderness, pyrexia, rash or eosinophilia as relevant on the AE form. Please note that treatment with trametinib often associates with rash which is usually acneiform and affects the scalp, face, neck, chest, and upper back. Discuss with Sponsor as needed.
- Record use of concomitant medications such as acetaminophen, herbal remedies, other over the counter medications, or putative hepatotoxins, on the concomitant medications form.

The following assessments are required for subjects with ALT $\geq 3 \times \text{ULN}$ and bilirubin $\geq 2 \times \text{ULN}$ ($>35\%$ direct) but are optional for other abnormal liver chemistries:

- Anti-nuclear antibody, anti-smooth muscle antibody, and Type 1 anti-liver kidney microsomal antibodies and quantitative total immunoglobulin G (IgG or gamma globulins).
- Liver imaging (ultrasound, magnetic resonance, or computerized tomography) to evaluate liver disease.
- Serum acetaminophen adduct assay (quantifies potential acetaminophen contribution to liver injury, detectable by HPLC assay more than 1 week following acetaminophen use).
- Only in those with underlying chronic hepatitis B at study entry (identified by positive hepatitis B surface antigen): quantitative hepatitis B DNA and hepatitis delta antibody. **NOTE:** if hepatitis delta antibody assay cannot be performed, it can be replaced with a PCR of hepatitis D RNA virus (where needed) – as outlined in: <http://www.ncbi.nlm.nih.gov/pmc/articles/PMC1153793/>.

5.6.1.1.15.3 Liver Chemistry Monitoring Criteria

For subjects with ALT $\geq 3 \times \text{ULN}$ **but** $< 8 \times \text{ULN}$ which exhibit a decrease to ALT $\geq 3 \times \text{ULN}$, but $< 5 \times \text{ULN}$ **and** bilirubin $< 2 \times \text{ULN}$, without hepatitis symptoms or rash, and who can be monitored weekly for 4 weeks, the following actions should be taken:

- Notify the Sponsor within 24 hours of learning of the abnormality to discuss subject safety
- Continue study treatment
- Return weekly for repeat liver chemistries (ALT, AST, alkaline phosphatase, bilirubin) until they resolve, stabilize or return to within baseline values

- If at any time the subject meets any of the liver chemistry stopping criteria 1 – 5, proceed as described above
- If, after 4 weeks of monitoring, ALT <3xULN and bilirubin <2xULN, monitor subjects twice monthly until liver chemistries normalize or return to within baseline values.

5.6.1.1.15.4 Drug Restart/Rechallenge Following Liver Events that are Possibly Related to Study Treatment

Approval by Sponsor for study treatment restart can be considered where:

The subject is receiving compelling benefit, benefit of drug restart exceeds risk, and no effective alternative therapy is available. Ethics Committee or Institutional Review Board approval of study treatment restart/rechallenge must be obtained, as required.

If the restart/rechallenge is approved by Sponsor in writing, the subject must be provided with a clear description of the possible benefits and risks of drug administration, including the possibility of recurrent, more severe liver injury or death.

The subject must also provide signed informed consent specifically for the study treatment restart/rechallenge. Documentation of informed consent must be recorded in the study chart.

Study treatment must be administered at the dose specified by Sponsor.

Subjects approved by the Sponsor for restart/rechallenge of study treatment must return to the clinic twice a week for liver chemistry tests until stable liver chemistries have been demonstrated and then laboratory monitoring may resume as per protocol.

5.6.1.1.15.5 Drug Restart Following Transient Resolving Liver Events Not Related to Study Treatment

Approval by Sponsor for drug restart can be considered where:

- Liver chemistries have a clear underlying cause (e.g., biliary obstruction, hypotension and liver chemistries have improved to normal or are within 1.5 x baseline and ALT <3xULN). Ethics Committee or Institutional Review Board approval of study treatment restart/rechallenge must be obtained, as required.
- If restart of study treatment is approved by Sponsor in writing, the subject must be provided with a clear description of the possible benefits and risks of drug administration, including the possibility of recurrent, more severe liver injury or death.
- The subject must also provide signed informed consent specifically for the restart. Documentation of informed consent must be recorded in the study chart.
- Study treatment must be administered at the dose specified by Sponsor.

Subjects approved by the Sponsor for restarting study treatment must return to the clinic once a week for liver chemistry tests until stable liver chemistries have been demonstrated and

then laboratory monitoring may resume as per protocol. If protocol defined stopping criteria for liver chemistry elevations are met, study treatment must be stopped.

A dose reduction below 75 mg BID for dabrafenib and 1 mg once daily for trametinib is not allowed. If a dose reduction below 75 mg BID for dabrafenib is required, dabrafenib will be permanently discontinued, but the subjects will be allowed to continue trametinib. If a dose reduction below 1 mg once daily for trametinib is required, then trametinib will be permanently discontinued, but these subjects will be allowed to continue dabrafenib.

Note: Approval from the Sponsor is required to restart study treatment after ≥ 21 days of interruption.

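### Table 30, row 2: a trigger for holding and possibly restarting dabrafenib/trametinib reaches outside its own row and overlaps the permanent-stop rules for raised AST/ALT with raised bilirubin

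*Combined protocol and SAP*

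**What the plan says.** Three places in Section 5.6.1.1.15 govern the same laboratory values.

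- **Table 30, row 2.** The label is "AST or ALT >5.0xULN to ≤8.0xULN without bilirubin elevation", and absence of elevation is defined as total bilirubin "≤2.0xULN, or direct bilirubin ≤35" per cent. The action cell reads "Hold dabrafenib, and/or trametinib if (any criteria are met" and lists three triggers: AST/ALT above 5.0xULN; "AST/ALT >3x ULN AND total bilirubin >2x ULN"; and total bilirubin above 3xULN. The hold lasts until recovery to Grade 1 or less. The cell then says: "After consultation with Sponsor, dabrafenib and/or trametinib may be restarted reduced by one dose level". Without such recovery within 2 weeks, study treatment ends permanently.
- **Table 30, row 3.** The label is "AST or ALT >3.0 x ULN with concomitant elevation in bilirubin", defined as total bilirubin "≥2.0 x ULN with direct bilirubin >35" per cent, or the meeting of any liver chemistry stopping criterion. The action is permanent discontinuation of all study treatment.
- **Section 5.6.1.1.15.1.** Criterion 1 is AST/ALT of at least 3xULN with bilirubin of at least 2xULN and more than 35% direct (or INR above 1.5). Its note covers missing fractionation: "If serum bilirubin fractionation is not immediately available, study treatment should be discontinued" on the AST/ALT and total bilirubin limits alone. Criterion 2 is AST/ALT of at least 8xULN. Meeting any criterion means immediate discontinuation and no rechallenge.

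Section 5.6.1.1.15.4 allows restart after a possibly related liver event in exceptional cases. It requires compelling benefit, no effective alternative, written Sponsor approval, ethics approval where required, specific signed consent and twice-weekly liver tests.

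**The concern.** The second row 2 trigger does not fit the row it sits in. The label describes subjects without bilirubin elevation and with AST/ALT above 5xULN. The trigger describes subjects with raised bilirubin and AST/ALT only above 3xULN, and it omits the direct-bilirubin condition that separates row 2 from row 3. A site that applies the trigger as written, rather than through the row label, arrives at a hold with possible restart for a profile that row 3 and criterion 1 treat as a permanent stop.

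At stake is which safeguards apply before re-exposure. Row 2 asks for recovery and a consultation with the Sponsor. After a stopping criterion, the only route back is the more demanding one in Section 5.6.1.1.15.4. Hepatotoxicity is foreseeable here: Section 4.2.1 reports that it ended a trial of another MAPK-inhibitor and immunotherapy combination. Section 8.2.1 keeps continuing Part 3 subjects on the protocol's dose modification guidelines, so the wording still applies to treated subjects.

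**Working it through.** There is no figure in the plan to reproduce. The check sets the rules side by side as logical conditions. Write A for AST/ALT in xULN, B for total bilirubin in xULN and D for the direct fraction.

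- Row 2 label: 5 < A ≤ 8 and (B ≤ 2.0 or D ≤ 35%)
- Row 2 triggers: A > 5, or (A > 3 and B > 2), or B > 3
- Row 3, bilirubin limb: A > 3, B ≥ 2.0 and D > 35%
- Criterion 1, bilirubin arm: A ≥ 3, B ≥ 2 and (D > 35% or D not available)
- Criterion 2: A ≥ 8

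**Step 1: inside the row 2 label.** The label requires A > 5, so the first trigger is always true. The two bilirubin triggers change nothing there and can act only on subjects outside the label.

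**Step 2: outside the label.** Compare the second trigger (A > 3 and B > 2) with row 3's bilirubin limb (A > 3, B ≥ 2.0, D > 35%). Every row 3 bilirubin case meets the trigger except those at B = 2.0. On a grid in steps of 0.1, with A from 1.0 to 12.0, B from 0.5 to 6.0 and D at 20% or 50%:

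- Row 3 points: 90 values of A (3.1 to 12.0) × 41 values of B (2.0 to 6.0) = 3690, all at D = 50%.
- Of these, meeting the second row 2 trigger: 90 × 40 = 3600. The other 90 are at B = 2.0.
- Of these, meeting the row 2 label: 30 values of A (5.1 to 8.0) × 1 value of B (2.0) = 30.

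These counts describe the rules, not how often subjects would meet them.

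**Step 3: example subjects.**

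| A | B | D | Row 2 label | Second row 2 trigger | Row 3 bilirubin limb | Criterion 1 | Criterion 2 |
|---|---|---|---|---|---|---|---|
| 4 | 2.5 | 50% | no | yes | yes | yes | no |
| 4 | 2.5 | 20% | no | yes | no | no | no |
| 4 | 2.5 | unknown | no | yes | undetermined | yes (note) | no |
| 6 | 2.5 | 20% | yes | yes | no | no | no |
| 6 | 2.5 | unknown | not established | yes | undetermined | yes (note) | no |
| 6 | 2.0 | 50% | yes | no | yes | yes | no |
| 8.0 | 1.0 | 20% | yes | no | no | no | yes |

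Lines 1, 3 and 5 show the trigger overlapping a permanent stop. Lines 2 and 4 show it working without conflict. Lines 6 and 7 are boundary collisions that remain when the labels are followed strictly: in line 6 both row labels are met, and in line 7 row 2's label and criterion 2 are both met.

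**Step 4: unfractionated bilirubin.** Row 3's second limb imports the stopping criteria, so the criterion 1 note does reach Table 30 and says discontinue. But the row 2 trigger also fires without a direct fraction. Footnote a of the table speaks only of performing fractionation and SAE reporting, and the note does not say what follows if the fraction later returns at 35% or below.

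**The case against.** The best defence is that a row label governs its row. With the labels applied, a subject with bilirubin above 2xULN and a known direct fraction above 35% belongs to row 3 only, and the overlap on the grid falls from 3600 points to 30. The unfractionated case also has an answer, through row 3's second limb. The row 2 triggers have legitimate uses too: direct fraction of 35% or less, or isolated bilirubin above 3xULN, where row 3's bilirubin limb is not met. All of this stands, and it limits the point. It does not explain why row 2 carries bilirubin triggers that are redundant within its label, and it does not touch the two boundary collisions.

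A reader might infer more than the documents support:

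- **That sites are told to restart.** Restart is permitted, after recovery and Sponsor consultation; it is not ordered.
- **That every Hy's Law case receives opposite orders.** The protocol defines that term on ALT, with more than 35% direct bilirubin or INR above 1.5. A fully characterised bilirubin-based case goes to row 3 under the labels.
- **That the stop route forbids any re-exposure.** Section 5.6.1.1.15.4 keeps an exceptional route open.
- **That the Week 36 interim endpoint is at risk**, because an adverse-event discontinuation is scored as PD. Sections 5.2.5 and 7.1.5.3 report that the Part 3 final analysis is complete, so a wording change cannot affect it.

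**Conclusion.** The point holds as an internal inconsistency in a safety table. Row 2's second trigger does not match its label, lacks the direct-bilirubin condition and, read alone, overlaps row 3 and criterion 1 for all row 3 bilirubin cases above 2.0xULN and for unfractionated cases. Under strict reading, the overlap on AST/ALT and bilirubin values is confined to total bilirubin of exactly 2.0xULN (direct above 35%, AST/ALT above 5 to 8xULN) and AST/ALT of exactly 8.0xULN. The practical risk is that a site reading the trigger as free-standing holds and restarts a subject whom row 3 would discontinue.

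The documents give no rate for such events and do not show that sites have diverged, so the number of subjects affected is unknown. The check covers AST/ALT, total bilirubin and direct fraction only; the INR arm of criterion 1 and criteria 3 to 5 were not mapped. It also assumes that the symbols and row alignment in the extracted table are right. Footnote a is visibly garbled, so they should be confirmed against the source file. Which clinical action is correct is not a question for this review.

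**What to change.** Reconcile rows 2 and 3 of Table 30 with the stopping criteria in Section 5.6.1.1.15.1, so that each combination of AST/ALT and bilirubin falls in exactly one row. Settle the boundary values (bilirubin 2.0xULN, AST/ALT 8.0xULN) explicitly. State the direct-bilirubin condition and the unfractionated case the same way in the row 2 triggers, row 3 and criterion 1, including what applies if the fraction arrives later. If the bilirubin triggers are meant for profiles outside row 2's present label, those profiles need a row of their own. The sponsor's clinicians decide which action is kept in each place.

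The cost is table wording in the next amendment, with no added tests or visits. Amendment 6 was itself a change to dose modification wording.
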